7.3 Adverse Event Characteristics

- **CTCAE term (AE description) and grade:** The descriptions and grading scales found in the revised NCI Common Terminology Criteria for Adverse Events (CTCAE) version 5.0 will be utilized for AE reporting. All appropriate

CONFIDENTIAL

This document is confidential. Do not disclose or use except as authorized.

treatment areas should have access to a copy of the CTCAE version 5.0. A copy of the CTCAE version 5.0 can be downloaded from the CTEP web site http://ctep.cancer.gov/protocolDevelopment/electronic_applications/ctc.htm.

- **For expedited reporting purposes only:**
 - AEs for the agent(s) that are listed above should be reported only if the adverse event varies in nature, intensity or frequency from the expected toxicity information which is provided.
 - Other AEs for the protocol that do not require expedited reporting are outlined in the next Section (Expedited Adverse Event Reporting) under the sub-heading of Protocol-Specific Expedited Adverse Event Reporting Exclusions.
- **Attribution** of the AE:
 - Definite – The AE is *clearly related* to the study treatment.
 - Probable – The AE is *likely related* to the study treatment.
 - Possible – The AE *may be related* to the study treatment.
 - Unlikely – The AE is *doubtfully related* to the study treatment.
 - Unrelated – The AE is *clearly NOT related* to the study treatment.

7.4 Adverse Event Reporting

7.4.1 In the event of an unanticipated problem or life-threatening complications treating investigators must immediately notify the Overall PI. Additionally, BMS must be notified within 24 hours.

BMS Contact:

SAE Email Address: [contact]
SAE [contact]

7.4.2 Investigators **must** report to the Overall PI any adverse event (AE) that occurs after the initial dose of study treatment, during treatment, or within 90 days of the last dose of treatment on the local institutional SAE form. Per BMS guidelines, Ipilimumab follow up for AE/SAEs is 90 days from the last dose of treatment.

7.4.3 DF/HCC Adverse Event Reporting Guidelines

Investigative sites within DF/HCC will report AEs directly to the DFCI Office for Human Research Studies (OHRS) per the DFCI IRB reporting policy.

7.4.4 Protocol-Specific Adverse Event Reporting Exclusions

For this protocol only, the AEs/grades listed below do not require expedited reporting to the Overall PI or the DFCI IRB. However, they still must be reported through the routine reporting mechanism (i.e. case report form).

CONFIDENTIAL

This document is confidential. Do not disclose or use except as authorized.

Events not considered to be serious adverse events are hospitalizations for:

- routine treatment or monitoring of the studied indication, not associated with any deterioration in condition, or for elective procedures
- elective or pre-planned treatment for a pre-existing condition that did not worsen
- emergency outpatient treatment for an event not fulfilling the serious criteria outlined above and not resulting in inpatient admission
- respite care

7.5 Reporting to the Food and Drug Administration (FDA)

The Overall PI, as study sponsor, will be responsible for all communications with the FDA. The Overall PI will report to the FDA, regardless of the site of occurrence, any serious adverse event that meets the FDA's criteria for expedited reporting following the reporting requirements and timelines set by the FDA.

7.6 Reporting to Hospital Risk Management

Participating investigators will report to their local Risk Management office any participant safety reports, sentinel events or unanticipated problems that require reporting per institutional policy.

7.7 Routine Adverse Event Reporting

All Adverse Events **must** be reported in routine study data submissions to the Overall PI on the toxicity case report forms. **AEs reported through expedited processes (e.g., reported to the IRB, FDA, etc.) must also be reported in routine study data submissions.**

8. PHARMACEUTICAL INFORMATION

A list of the adverse events and potential risks associated with the investigational or other agents administered in this study can be found in **Section 6**.

8.1 Ipilimumab

CONFIDENTIAL

This document is confidential. Do not disclose or use except as authorized.

Bristol-Myers Squibb Inc. (BMS) supplies distributes Ipilimumab at no cost for this study.

8.1.1.1 Description

Chemical Name or Amino Acid Sequence: 4 polypeptide chains, 2 identical heavy chains with 447 amino acids and 2 identical light chains consisting of 215 amino acids.

Other Names: Anti-CTLA-4 monoclonal antibody, MDX-010

Classification: Human monoclonal antibody

M.W.: 147,991 Daltons

Mode of Action: Ipilimumab is specific for the CTLA-4 antigen expressed on a subset of activated T-cells. CTLA-4 interaction with the B7 molecule, one of its ligands expressed on professional antigen presenting cells, can down-regulate T-cell response. Ipilimumab is thought to act by blocking the interaction of CTLA-4 with the B7 ligand, resulting in a blockade of the inhibitory effect of T-cell activation. The CTLA-4/B7 creates the interaction.

Description: Ipilimumab is a fully human immunoglobulin (IgG1) with two manufacturing processes – ongoing trials have been using substances manufactured using Process B. New clinical trials will be using Ipilimumab that is manufactured by Process C. The Process C has been developed using a higher producing subclone of the current Master Cell Bank, and modified cell culture and purification steps.

8.1.2 Form

Ipilimumab will be provided in open-label containers. Container labels will contain the batch number, contents, storage conditions, and Investigational New Drug caution.

Ipilimumab is available as a 200 mg /40 mL or 50 mg /10 mL (5 mg/mL) single-use vial. The vial is a clear, colorless, sterile, isotonic aqueous solution (pH of 7) that may contain particles. Each vial is a Type I flint glass vial with gray butyl stoppers and sealed with aluminum seals.

Component	Process C	
	50 mg/ vial^a	50 mg/ vial^a
Ipilimumab	53.5 mg	213 mg
Sodium Chloride, USP	62.6 mg	249 mg
TRIS-hydrochloride	33.7 mg	134.3 mg
Diethylenetriamine pentacetic acid	0.42 mg	1.67 mg
Mannitol, USP	107 mg	426 mg
Polysorbate 80 (plant-derived)	1.18 mg	4.69 mg
Sodium Hydroxide	QS to pH 7	
Hydrochloric acid	QS to pH 7	
Water for Injection	QS: 10.7 mL	QS: 42.6 mL

CONFIDENTIAL

This document is confidential. Do not disclose or use except as authorized.

Nitrogen ^c	Processing agent
-----------------------	------------------

^aIncludes 0.7 overfill; ^bIncludes 2.6 mL overfill.

^cNitrogen is used to transfer the bulk solution through the pre-filled and sterilizing filters into the aseptic area.

8.1.3 Storage and Stability

Storage: Store intact vials refrigerated at (2-8° C), protected from light. Do not freeze.

Stability: Shelf-life surveillance of the intact vials is ongoing. Solution as described above is stable up to 24 hours refrigerated at (2-8° C) or at room temperature/ room light.

CAUTION: Ipilimumab does not contain antibacterial preservatives. Use prepared IV solution immediately. Discard partially used vials.

8.1.4 Compatibility

Ipilimumab will be administered individually on this study, and thus issues of compatibility with other agents are not anticipated.

8.1.5 Handling

The investigational product must be stored in a secure area according to local regulations. The investigator is responsible for ensuring that it is dispensed only to study subjects. The investigational product must be dispensed only from official study sites by authorized personnel according to local regulations. The investigator must ensure that the investigational product is stored in accordance with the environmental conditions (temperature, light, and humidity) determined by the sponsor. If concerns regarding the quality or appearance of the investigational product arise, the investigational product must not be dispensed and BMS must be contacted immediately, via:

**[name]
Project Manager, Syneos Health
Providing services to Bristol-Myers Squibb
[name]
[name]**

syneoshealth.com

Ipilimumab (BMS-734016) Injection (5 mg/ml), must be stored refrigerated (2°C - 8°C) with protection from light. In preparation of infusion, Ipilimumab may be stored in IV infusion bags (PVC, non-PVC/non-DEHP) or glass infusion containers at room temperature or refrigerated (2°C - 8°C) for up to 24 hours. Drug must be

CONFIDENTIAL

This document is confidential. Do not disclose or use except as authorized.

completely delivered to the subject within 24 hours of preparation. This includes any time in transit plus the total time for the infusion.

As with all injectable drugs, care should be taken when handling and preparing Ipilimumab. Whenever possible, it should be prepared in a laminar flow hood or safety cabinet using standard precautions for the safe handling of intravenous agents, applying aseptic technique. Gloves are required. If Ipilimumab concentrate or solution comes in contact with skin or mucosa, immediately and thoroughly wash with soap and water. After final drug reconciliation, unused Ipilimumab solution should be disposed of at the site following procedures for the disposal of anticancer drugs.

8.1.6 Availability

Ipilimumab is an investigational agent supplied by BMS.

8.1.7 Preparation and Administration

The following instructions are suggested guidelines for preparation of Ipilimumab which may be prepared per institutional standards and package insert. The supplies needed for Ipilimumab preparation and administration include calibrated syringes and infusion containers. Ipilimumab is to be administered as an IV infusion over 90 +/-10 minutes through an IV line containing a sterile, nonpyrogenic, low-protein-binding in-line filter per institutional standard practice. Flush IV line with NS or D5W after each dose per institutional standard practice. The total dose for each subject's first Ipilimumab infusion (Cycle 1, Day 1) must be calculated using the most recent subject weight (obtained within 3 days of the dosing visit, and prior to the infusion). The same total dose may be given in the subsequent infusions if the most recent subject weight (obtained within 3 days of dosing visit, and prior to the infusion) is within 5% of the subject weight prior to the first infusion. If the most recent subject weight (obtained within 3 days of the dosing visit, and prior to the infusion) at a subsequent dosing visit is **not** within 5% of the subject weight prior to the first infusion, the total dose must be recalculated based on the most recent subject weight for that dosing visit.

- 1) As Ipilimumab is stored at refrigerated temperatures (2 - 8°C), allow the appropriate number of vials of Ipilimumab to stand at room temperature for approximately 5 minutes.
- 2) Aseptically withdraw the required volume of Ipilimumab solution into a syringe. Insert the needle at an angle into the Ipilimumab vial by placing the needle bevel side down against the glass, with the tip touching the neck of the vial. The initial solution concentration is 5 mg/mL. [Note: A sufficient excess of Ipilimumab is incorporated into each vial to account for withdrawal losses].

CONFIDENTIAL

This document is confidential. Do not disclose or use except as authorized.

- 3) Ensure that the Ipilimumab solution is clear, colorless, and essentially free from particulate matter on visual inspection. If multiple vials are needed for a subject, it is important to use a separate sterile syringe and needle for each vial to prevent problems such as dulling of needle tip, stopper coring, repeated friction of plunger against syringe barrel wall, and so on.
- 4) Preparation of ipilimumab will follow package insert and/or institutional standard practice.
- 5) Mix by GENTLY inverting several times. DO NOT shake.
- 6) Visually inspect the final solution. If the initial diluted solution or final dilution for infusion is not clear, or the contents appear to contain precipitate, the solution should be discarded.
- 7) Do not draw into each vial more than once. Any partial vials should be safely discarded and should not be stored for reuse.
- 8) Ipilimumab should be administered under the supervision of a physician experienced in the use of intravenous agents. Ipilimumab is administered as an intravenous infusion only.
- 9) Ipilimumab is administered over 90 +/- 10 minutes, and hydration is allowed but not required per protocol. Patients should be observed closely for infusion reactions during treatment, with vital signs checked at least every 30 minutes, including after an observation period of 30 minutes after completing the infusion. A detailed description of common infusion reactions and their management is outlined in **Section 6.1.11**

8.1.8 Ordering

Ipilimumab will be provided by BMS. Investigational supplies of study drug will be provided to DFCI research pharmacy as per standard procedures and agreements with BMS.

BMS protocol#: CA184-559
BMS vendor contact for drug orders is
[contact]

8.1.9 Accountability

The investigator, or a responsible party designated by the investigator, should maintain

CONFIDENTIAL

This document is confidential. Do not disclose or use except as authorized.

a careful record of the inventory and disposition of the agent using a drug accountability form.

8.1.10 Destruction and Return

Expired ipilimumab supplies will be destroyed on site per SOP. At the end of the study, unused supplies of ipilimumab will be destroyed on site per SOP. Destruction will be documented in the computerized institutional Drug Accountability Record Form.

9. CORRELATIVE STUDIES

9.1 Laboratory Correlative Study Sample Collection

All laboratory tests are mandatory and will be processed at the Cell Manipulation Core Facility at DFCI. Please refer to the study operations manual for details regarding processing and shipping study specimens.

Samples will be obtained pre-dose at screening or Cycle 1 Day 1 (C1D1), per the schema in the required data table (**Table 6**).

9.1.1 Peripheral Blood Correlatives

Each time point will require a PASQ3P (three - 10mL EDTA tubes) for correlative analysis. These research tubes will preferably be drawn at the same time as clinical labs drawn at the below time points, though can be drawn at an alternative time for scheduling convenience. There are two exceptions:

- a) Cycle 1 Day 1 (C1D1):** Order a PASQ6P – six – 10mL EDTA tubes. Each lab involved requires a baseline sample. This needs to be collected prior to the patient receiving any study treatment.
- b) Cycle 3 Day 1, Cycle 4 Day 29, Cycle 5 Day 1, Cycle 6 Day 1, Cycle 8 Day 1, Off Rx:** For every time point when a BM aspirate is collected, instead of collecting a PASQ3P (three-10mL EDTA tubes) order a PASQ4P (four-10 mL EDTA tubes).

9.1.2 Bone Marrow Aspirate and Biopsy

Bone marrow aspirate and biopsy samples will be obtained per the schema in the required data table (**Tables 6, 7**). Two-10 mL research bone marrow aspirates and one bone marrow core biopsy should be collected for correlatives at each time point a biopsy is noted in the study calendar below.

CONFIDENTIAL

This document is confidential. Do not disclose or use except as authorized.

9.1.3 Skin/Extra-Medullary Disease Biopsies

Skin/other sites of extra-medullary disease will also be biopsied per the required data table schema, if deemed safe and clinically feasible. Tissue should be sent in a sterile, leak proof container that contains DMEM at room temperature to the TIGL. Sample should be delivered within 4 hours and be at least 3 mm in diameter.

Archival tissue from patients on study may be utilized for correlative studies as necessary.

9.2 Planned Correlative Studies

The goals of the correlative analyses include:

To assess the immunologic impact of infusions of CD25/Treg-depleted DLI plus Ipilimumab. These include immunophenotypic analysis of T-cell subsets, B and NK cells; phenotypic and functional readouts of effector T (Teff) and regulatory T (Treg) cell activation status; changes in plasma cytokines and chemokines; tumor microenvironment; and tumor mutation profile. We also seek to correlate clinical response with changes in circulating Teff vs. Treg cell counts and activation; the persistence of adoptively transferred Teff cells; changes in cytokine and chemokine levels; tumor infiltration by activated CD8⁺ T cells; and tumor mutation profile, blast phenotype and tumor microenvironment. In an exploratory analysis, we will perform tumor neoantigen discovery to identify novel T cell targets and correlate tumor mutational load with response.

The specific studies include:

- Assessment of donor cell chimerism (molecular testing and cell based assays).
- Immune cell frequencies and numbers (flowcytometry, mass cytometry, immune histochemistry).
- CD4 Teff and Treg, CD8 T, and NK cell frequency, number, phenotype, proliferation (flow or mass cytometry).
- Teff cell function assays and phenotypic readouts in vivo and in vitro.
- Teff TCR sequencing
- Teff, Treg, CD8 T, NK cell gene expression / transcriptome profiling.
- Next generation sequencing of measurable residual disease.
- AML/MDS/MPN immune-evasion assessments (flow or mass cytometry, genome sequencing of baseline and relapse samples, including non-malignant tissue).
- Serum cytokine, chemokine assessments

Samples will be collected at time points mentioned above (**Tables 6, 7**).

CONFIDENTIAL

This document is confidential. Do not disclose or use except as authorized.

10. STUDY CALENDAR

Baseline disease assessments (e.g. BM, Scans), cardiac/pulmonary evaluations, and Labs/IDM must be done ≤ 4 weeks prior to the start of therapy. Baseline other labs (e.g. CBC, chemistries) should be repeated within 1 week prior to start of therapy. In the event that the participant's condition is deteriorating, laboratory evaluations should be repeated within 48 hours prior to initiation of the next cycle of therapy.

There will be at least one-week interval between consecutive enrollments at the same dose level during phase 1A. All assessments must be performed prior to administration of any study medication. All study assessments should be performed within ± 3 days of the protocol-specified date during induction and ± 7 days during maintenance, unless otherwise noted. Ipilimumab should be administered within ± 3 days of the protocol-specified date during induction (**Table 6**) and ± 7 days during maintenance (**Table 7**), unless otherwise noted. Note that in the calendar below, entry to maintenance Ipilimumab during weeks 24-60 are only for patients with stable disease or better at time of Cycle 4 day 29 (D92) response assessment time point.

CONFIDENTIAL

This document is confidential. Do not disclose or use except as authorized.

Table 6: Induction Phase										
		Screening	C1 D1 (D1)	C1 D8 (D8)	C1 D15 (D15)	C2 D1 (D22)	C2 D8 (D29)	C3 D1 (D43) (DLT Endpoint)	C4 D1 (D64)	C4 D29 (D92) (Response Endpoint)
CD25/Treg depleted DLI			X							
Ipilimumab*			X			X		X	X	
Informed Consent		X								
EKG ¹		X								
Cardiac Evaluation ^{1,2}		X								
PFT		X								X
β-HCG Test ³		X								
Complete History		X								
Interval History			X	X	X	X	X	X	X	X
Physical exam (Ht, Wt, VS ⁴ , PS)		X ⁴	X	X	X	X	X	X	X	X
CBC and differential		X	X	X	X	X	X	X	X	X
Serum Chemistry ⁵		X	X	X	X	X	X	X	X	X
TSH		X								X
Chimerism testing		X						X		X
PB Correlative studies ⁶		X	X ¹¹	X	X	X	X	X ¹²	X	X ¹²
BM aspirate and core ⁷		X						X		X
aGVHD assessment ⁸		X	X	X	X	X	X	X	X	X
cGVHD assessment ⁹		X						X		X
Viral Panel ¹⁰		X								

Table 7: Maintenance Phase (For patients with SD/PR/CR at D92 Response Assessment)											Off Rx**
	C4 D57	C5 D1 (Wk 24)	C5 D29	C5 D57	C6 D1 (Wk 36)	C6 D29	C6 D57	C7 D1 (Wk 48)	C7 D29	C7 D57	C8D1 (Wk 60) and beyond
Ipilimumab		X			X			X			X
PFT		X			X			X			X
Complete History											X
Interval History	X	X	X	X	X	X	X	X	X	X	
Physical exam ⁴ (Ht, Wt, VS, PS)	X	X	X	X	X	X	X	X	X	X	X
CBC and differential	X	X	X	X	X	X	X	X	X	X	X
Serum Chemistry ⁵	X	X	X	X	X	X	X	X	X	X	X
TSH											X
Chimerism testing		X									X
PB Correlative studies ⁶	X	X ¹²			X ¹²			X			X ¹²
BM aspirate and core ⁷		X			X						X
aGVHD assessment ⁸	X	X	X	X	X	X		X	X	X	X
cGVHD assessment ⁹		X			X			X			X

CONFIDENTIAL

This document is confidential. Do not disclose or use except as authorized.

- * – Patients will be dosed at start of week 1, 4, 7, and 10 (induction) and return for an end of induction response evaluation on start of week 14. Maintenance dosing will then occur at weeks 24, 36, 48 and 60. Patients who experience clinical benefit may continue to receive Ipilimumab q12 weeks till week 60 unless there is unacceptable toxicity, disease progression, or withdrawal of consent.
- **– End of study off-treatment visit will be 3 months after last dose of maintenance Ipilimumab. Note: for IND/IDE trials, follow up visits or other contact are required in order to identify SAEs during the 30 days following the end of study treatment
- 1 – A baseline EKG and cardiac ECHO (or MUGA) is required for all patients, and anytime thereafter as clinically indicated.
- 2 – For those with evidence of CHF, myocardial infarction, myocarditis or cardiomyopathy at any time during the study, a detailed cardiac evaluation including labs (CPK, Troponin), cardiology consult, with EKG and ECHO (or MUGA) at minimum is required, as clinically indicated. Please refer to **Section 6.1.13** for guidance on cardiac toxicity management for Ipilimumab.
- 3 – For females of childbearing potential only
- 4 – O_2 Saturation on room air required only at screening; Weight on day closest prior to infusion will be used for study dosing calculations, height only needs to be collected at screening.
- 5 – Includes: comprehensive metabolic panel, LFTs, magnesium, phosphorus, uric acid, LDH, lipase, eGFR
- 6 – See **Section 9.1.1**.
- 7 – See **Section 9.1.2 and 9.1.3**. If there is no bone marrow involvement at baseline and/or extra-medullary disease is documented, the other sites of disease relapse will be assessed as clinically appropriate (**section 9.1.3** e.g. measurement of lesions of leukemia cutis including skin biopsy, PET/CT assessments for other extramedullary sites (e.g. granulocytic sarcoma)
- 8 – See **Appendix C** for aGVHD assessment
- 9 – Per NIH consensus criteria for cGVHD assessment
- 10 – Viral Panel includes HIV, Hep B and C
- 11 – Exception under 9.1.1 a). Draw a PASQ6P
- 12 – Exception under 9.1.1 b). Draw a PASQ4P

Supplemental Scheduling Table			
Induction Phase	Total Days	Maintenance Phase	Total Days
Cycle 1 Day 1 (Ipi)	1	Cycle 4 Day 57	120
Cycle 1 Day 8	8	Cycle 5 Day 1 (Ipi)	169
Cycle 1 Day 15	15	Cycle 6 Day 1 (Ipi)	253
Cycle 2 Day 1 (Ipi)	22	Cycle 7 Day 1 (Ipi)	337
Cycle 2 Day 8	29	Cycle 8 Day 1 (Ipi)	421
Cycle 3 Day 1 (Ipi)	43	Off Treatment	
Cycle 4 Day 1 (Ipi)	64		
Cycle 4 Day 29	92		

*Induction Phase +/- 3 days for appointment window

**Maintenance Phase +/- 7 days for appointment window

***Patients who do not complete the entirety of the Induction and Maintenance (8 cycles) phases are not required to complete the Off-Treatment visit outlined in the Study Calendar. However, any corresponding data that can be gathered through Stand of Care appointments should be collected. Toxicities will be recorded until 3 months after the last dose of Ipilimumab.

CONFIDENTIAL

This document is confidential. Do not disclose or use except as authorized.

11. MEASUREMENT OF EFFECT / CLINICAL RESPONSE

Evaluable for toxicity- Participants who receive cell infusion at the specified dose plus Ipilimumab will be evaluated for toxicity. Evaluable patients are those who experience a DLT before day 43, or are assessable for DLT at day 43. Phase 1a patients who are unevaluable for DLT may be replaced.

Evaluable for response- Only those participants who have measurable disease present at baseline, have received cell infusion at the specified dose and least two cycles of Ipilimumab therapy, and have had their disease re-evaluated will be considered evaluable for response. These participants will have their response classified according to the disease-specific definitions stated in **Appendices E-F**. Patients unevaluable for response will not be replaced.

Response Criteria will be disease-specific, and are provided in detail in the following appendices:

- **Appendix E:** Acute Myelogenous Leukemia
- **Appendix F:** Myelodysplastic Syndrome / Myeloproliferative Neoplasm

Evaluation of Best Overall Response The best overall response is the best response recorded from the start of the treatment until disease progression/recurrence (taking as reference for progressive disease the smallest measurements recorded since the treatment started). The participant's best response assignment will depend on the achievement of both measurement and confirmation criteria

Duration of overall response: The duration of overall response is measured from the time measurement criteria are met for CR or PR (whichever is first recorded) until the first date that recurrence or PD is objectively documented, taking as reference for PD the smallest measurements recorded since the treatment started.

Duration of overall complete response: The duration of overall CR is measured from the time measurement criteria are first met for CR until the first date that recurrent disease is objectively documented.

Progression-Free Survival (PFS) is defined as the duration of time from start of treatment to time of objective disease progression or death whichever occurs first.

Overall Survival (OS) is defined as the duration of time from start of treatment to time of death.

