13.3 Secondary endpoints

- ORR (To determine complete remission (CR/CRi) rate at 6 weeks (day 43) after the cell infusion plus Ipilimumab)
- To determine the rate of progression-free survival (PFS) and overall survival (OS) at ~3 months (day 92) post cell infusion plus Ipilimumab
- To determine the rate of progression-free survival (PFS) and overall survival (OS) at ~ 1-year (60 weeks) post cell infusion plus Ipilimumab
- To determine the incidence and severity of acute GVHD rates after cell infusion plus Ipilimumab
- To determine the incidence and severity of chronic GVHD rates after cell infusion plus Ipilimumab

CONFIDENTIAL

This document is confidential. Do not disclose or use except as authorized.

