13.7 Analysis plan

Due to limited sample size, the analysis will be primarily descriptive. AEs/SAEs will be summarized by patient, type and grade as defined by the CTCAE v4.0. Rates will be described as proportions with exact binomial confidence intervals. CR/CRI rate at day 43 also will be described as a proportion with exact binomial confidence interval. Kaplan-Meier models will be used to estimate PFS and OS at day 100 and 1 year with exact pointwise confidence intervals. Acute and chronic GVHD will be described as cumulative incidence in the competing risks framework treating death without GVHD as a competing event. The association between clinical outcomes (response, PFS and OS and acute or chronic GVHD) and correlative endpoints (e.g., circulating Teff and Treg cells, number of AML/MDS/MPN blasts and other characteristics of the BM microenvironment pre-therapy and at post-treatment relapse) will be explored using univariable Cox, Fine and Gray regression analysis or exact Wilcoxon-Rank-Sum test, as appropriate. Analyses will be carried out in SAS 9.4 or R 3.3.2 or higher.

CONFIDENTIAL

This document is confidential. Do not disclose or use except as authorized.

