-Subjects who fail to achieve CR, Cri, or PR and who do not have criteria for PD will be defined as having the stable disease. If the subject dies prior to response assessment at the end of Cycle 1, then they will be classified as “indeterminate”.

E.1.7 Progressive disease (PD): may be defined as ONE of the following:

- $> 50\%$ increase in peripheral blood or bone marrow blasts from best assessment with minimum threshold of 20% blasts in the marrow or $1.0 \times 10^9/L$ blasts in peripheral blood.

-Development of biopsy proven extramedullary leukemia (if the subject has extramedullary

CONFIDENTIAL

This document is confidential. Do not disclose or use except as authorized.

disease at baseline, then PD will be defined by blood and marrow criteria or if new sites of extramedullary disease appear).

-If subject who present with an initial marrow blast percentage sufficiently high to preclude the ability to base disease progression on a >50% increase in marrow blast percentage, disease progression should be based on peripheral blood criteria or development of extramedullary leukemia as above.

E.1.8 Persistent Disease

Hematologic Persistence – Bone marrow or peripheral blasts >5% after d+30 following HCT

CONFIDENTIAL

This document is confidential. Do not disclose or use except as authorized.

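### No denominator is named for the day-43 CR/CRi rate, and the only response set the plan defines can drop early failures instead of counting them as non-responders

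*Combined protocol and SAP*

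**What the plan says.** The day-43 remission rate is the first secondary objective in Section 1.3. Section 13.3 repeats it: "To determine complete remission (CR/CRi) rate at 6 weeks (day 43) after the cell infusion plus Ipilimumab". The analysis in Section 13.7 is one sentence: "CR/CRI rate at day 43 also will be described as a proportion with exact binomial confidence interval". None of the three sections names an analysis set or points to one.

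Section 11 holds the only definition of who is evaluable for response. It begins: "Only those participants who have measurable disease present at baseline, have received cell infusion at the specified dose and least two cycles of Ipilimumab therapy". The remaining condition is a repeat disease assessment, and only patients who meet every condition are sent to the response criteria of Appendices E and F. On replacement, Section 11 says: "Patients unevaluable for response will not be replaced".

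Appendix E (E.1.6) assigns the label indeterminate to one kind of early failure in AML, in a sentence that opens: "If the subject dies prior to response assessment at the end of Cycle 1, then they will be classified as". It does not say whether such a patient is in the denominator. Appendix F has no early-death rule for MDS/MPN.

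**The concern.** A binomial proportion without a stated denominator is not fully specified. The natural reading is that the Section 11 set supplies it. That is an inference, because Section 13.7 does not refer to Section 11.

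On that reading, membership depends partly on outcome. Measurable disease is a baseline condition and the infused cell dose is fixed on day 1; neither is a problem. Two ipilimumab cycles and a disease re-evaluation can be known only later. Patients who fail fastest are the least likely to meet them, and they would be removed rather than counted as failures.

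The plan expects early losses. Section 13.4 deals with patients who die of progression, or progress and need removal, within the six-week window, and says how they count for the MTD. No section says how they count for response.

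Phase 1b exists partly to describe preliminary efficacy. The background figure a reader would set beside it, the 60% response at the higher cell dose in Section 2.2.1, is 9 of all 15 patients given that dose. A rate on the Section 11 set would have a more selective denominator.

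**Working it through.** The plan gives no target rate, power or sample size for CR/CRi, so there is no stated figure to reproduce. The check has two parts: who can fall out of the set, and how far the rate could move.

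**Who can fall out**

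- Dose 2 is on day 22 (Section 1.1 and the Supplemental Scheduling Table).
- Dosing stops for unacceptable toxicity or symptomatic progression (Section 5.1.4). Patients who need other treatment for progression leave the study (Section 5.1.7). Acute GVHD of grade 2 or higher needing systemic immunosuppression blocks the next cycle (Section 5.2.2).
- A toxicity hold alone need not exclude anyone. Section 6.1.3 allows an induction delay of up to 3 weeks, so dose 2 could fall as late as day 22 + 21 = day 43.
- A patient who progresses after dose 2, with a documented re-evaluation, stays in.
- An AML patient who dies before the end-of-Cycle-1 assessment has not had two cycles, so Section 11 would not classify that patient at all, while Appendix E assigns a label.
- The first scheduled on-treatment marrow is day 43 (Table 6). The Section 9.1.1 list covering "For every time point when a BM aspirate is collected" likewise begins at Cycle 3 Day 1. Appendix E's end-of-Cycle-1 time point therefore has no scheduled marrow, and the counting of a death between day 22 and day 43 is not stated.

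**How far the rate can move**

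Let N be the patients treated, r the responders and k the patients excluded. If all k are non-responders, the rate changes from r/N to r/(N-k), a factor of N/(N-k).

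N = 15 is the 5 dose-level-0 patients of phase 1a plus the 10 of phase 1b (Section 13.4 with its amendments); pooling them is an assumption. N = 10 is phase 1b alone.

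| k | N = 15 | N = 10 |
|---|---|---|
| 1 | 15/14 = 1.07 | 10/9 = 1.11 |
| 2 | 15/13 = 1.15 | 10/8 = 1.25 |
| 3 | 15/12 = 1.25 | 10/7 = 1.43 |

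Illustration with r = 4 (assumed) and Clopper-Pearson 95% intervals, the exact type named in Section 13.7:

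| Denominator | Rate | 95% CI | Shift (points) |
|---|---|---|---|
| All treated, 4/15 | 26.7% | 7.8 to 55.1 | reference |
| 1 non-responder out, 4/14 | 28.6% | 8.4 to 58.1 | +1.9 |
| 2 non-responders out, 4/13 | 30.8% | 9.1 to 61.4 | +4.1 |
| 3 non-responders out, 4/12 | 33.3% | 9.9 to 65.1 | +6.7 |
| 1 out, a responder, 3/14 | 21.4% | 4.7 to 50.8 | -5.2 |
| 3 out, one a responder, 3/12 | 25.0% | 5.5 to 57.2 | -1.7 |

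With N = 15 and k = 3 non-responders excluded, the shift is r/12 - r/15 = r/60: +3.3 points for r = 2 and +10.0 points for r = 6. For phase 1b alone with r = 3, 3/10 = 30.0% (6.7 to 65.2) becomes 3/7 = 42.9% (9.9 to 81.6).

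For scale, the interval at 4/15 is 55.1 - 7.8 = 47.3 points wide.

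**The case against.** The case for leaving the plan alone has five parts.

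- **Protocol and analysis plan are one document.** If Section 11 governs, the denominator is pre-specified. If it does not, only a cross-reference is missing. Either way something needs mending: the first reading gives a set that depends on outcome, the second leaves the choice open until results are known.
- **Few patients are at risk.** The 5 phase 1a patients at dose level 0 were all evaluable for DLT. Escalation after the first 3 required no DLT among them, and the last 2 had none, so all 5 appear to have been assessable at day 43. This stands: almost all exclusions would have to come from the 10 phase 1b patients, who are not replaced. One to three losses among 10 remain possible.
- **Direction is uncertain.** Patients stopped for toxicity or GVHD may include responders, and one excluded responder reverses the sign in the examples above. This stands, so the rate can be biased upward but need not be.
- **Early failures show elsewhere.** PFS and OS run from the start of treatment and include them. This limits the harm but does not repair the response rate. Reading indeterminate as non-CR would also help, but Appendix E does not say so.
- **The change comes late.** Phase 1b was cleared to proceed in June 2021 and this version is dated June 2023, in an open-label single-center trial. Outcomes may already be visible. That is a reason to date the change and report both denominators, not to leave the denominator unstated.

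**Conclusion.** The concern holds. The plan names no denominator for its first secondary endpoint, and the only response rule it contains would leave out early deaths, early progressions, early removals and patients never reassessed.

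An upward bias requires that the Section 11 set is used and that those excluded are mainly non-responders. The consequence is modest: the endpoint is secondary and descriptive, the MTD and recommended Phase II dose rest on DLT counts, and the shifts are small beside the interval width. Wide intervals, however, express sampling error and do not cover an unstated choice of denominator. The change should be made, but it is not critical to the trial's dose conclusions.

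**What to change.** In Sections 11 and 13.7:

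1. Define the primary CR/CRi denominator as all patients with measurable disease at baseline who received the study cell infusion at the specified dose and at least one dose of ipilimumab.
2. Count as a non-responder any patient without documented CR/CRi at the day-43 assessment, within the protocol's own window of 3 days either side. State that this includes early death, the Appendix E indeterminate category, progression, removal and absence of re-evaluation.
3. Report the present Section 11 evaluable set as a sensitivity analysis, with the number excluded and the reasons.
4. Date the change and say whether response data had been seen.

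This needs wording only. Screening and day-43 marrows are already scheduled in Table 6, and no treatment rule changes. The costs are a somewhat lower reported rate if early failures occur, and that a responder with no day-43 assessment counts as a failure. The sensitivity analysis would show such a patient if two cycles were given and a later re-evaluation exists.
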